### 8.2.2. EASI Components

The 4 EASI component scores (erythema, oedema/papulation, excoriation and lichenification) will be summarised by treatment and visit for the FAS. Summaries will present the descriptive statistics for baseline, change from baseline and percentage change from baseline data.

Percent change from baseline to Week 2 for each EASI component will be analysed for the FAS with an ANCOVA model. The model will include baseline value and treatment. The treatment effect will be estimated with the difference between least square means (LS means), defined as ZPL521 - placebo. The estimate, standard error, 1-sided p-value, and 90% CI will be presented.

The analysis will be repeated for all other time points (Day 5, Day 8 [Week 1] and Day 10).

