Subjects may withdraw from the study at any time without penalty and for any reason without prejudice to their future medical care. In all cases, the reason(s) for withdrawal, including the primary reason, must be recorded on the case report form (CRF). If a subject is prematurely withdrawn from the study for any reason, the investigator must make every effort to perform the evaluations described for the early termination/follow up visit (in clinic) and a further follow up contact (either by telephone or in clinic) 7 to 14 days later. Subjects who withdraw due to lack of efficacy (Cohort 3) or adverse events which may be attributed to double blind treatment will not be replaced.

Cohort 3 patients who withdraw due to personal reasons, poor compliance, other protocol deviations or are lost to follow up may be replaced until at least 30 evaluable patients have completed the study.

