#### 3.3. DETERMINATION OF SAMPLE SIZE

The sample sizes for Cohorts 1 and 2 are not based on formal statistical testing. Their sample sizes are considered sufficient to obtain suitable safety, tolerability and PK data prior to starting Cohort 3.

For Cohort 3 the sample size of 30 subjects has been determined on the basis of comparing the mean ZPL-5212372 Week 2 percentage change from baseline in the Eczema Area and Severity Index (EASI) score to that for placebo. With 20 subjects in the ZPL-5212372 group and 10 subjects in the placebo group, there is 80% power of obtaining a statistically significant result, assuming that there is an improvement of at least 30% with ZPL-5212372 compared to placebo and a standard deviation for the percentage changes from baseline between subjects of 30%. This is based on the analyses described and a 1-sided test at the 5% level of significance.

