#### **EASI Components**

A score for the EASI components (erythema [E], oedema/papulation [O], excoriation [X] and lichenification [L]) will be calculated across the body regions in a similar way to the calculation of the EASI total score. For example:

Erythema= $[0.1xE_{head}XExtent_{head}]$ +  $[0.2xE_{arms}XExtent_{arms}]$ +  $[0.3xE_{trunk}XExtent_{trunk}]$ + $[0.4xE_{legs}XExtent_{legs}]$ 

The secondary endpoints associated with Cohort 3 are percentage change from baseline for each of the EASI components (erythema, oedema/papulation, excoriation and lichenification).

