### 6. GENERAL ASPECTS FOR STATISTICAL ANALYSIS

#### 6.1. GENERAL METHODS

All statistical tests for Cohort 3 will be 1-sided at the 0.05 level of significance and accompanied by a 2-sided 90% CI. There will not be any adjustments for multiple comparisons. No statistical testing will be performed with the data from Cohorts 1 and 2.

All summaries and listings will be presented by treatment group and by cohort. For Cohorts 1 and 2, adverse events and pharmacokinetic data will be presented by treatment group and BSA treated (10%, 40% and overall) to assess whether BSA impacts this data.

Only on-treatment records will be summarised for post-baseline visits, except follow-up, unless stated otherwise. A record is considered on-treatment if it is on or before the date of last study medication plus 1 day.

Continuous variables will be summarised using the number of observations (n), mean, standard deviation (SD), 95% Confidence interval (CI) of mean, median, minimum, and maximum. Geometric mean and coefficient of variation (CV) will be included for PK parameters, where appropriate. Categorical variables will be summarised using frequencies and percentages. The number of missing values will be presented in summary tables. The missing count will not include

SAP Version v2.0 Page 22 of 43

Date: 16th March 2017

subjects who have discontinued at earlier visits.

Unless otherwise specified, the estimated mean and median for a set of values should be printed out to 1 more decimal place than the original values, and standard deviations should be printed out to 2 more decimal places than the original values. The minimum and maximum should report the same number of decimal places as the original values. The coefficient of variation will always be reported as a percentage to 1 decimal place. Percentages will be displayed with 1 decimal place; except percentages will not be presented when the count is zero and 100% will be presented as an integer.

Unless stated otherwise, baseline will be defined as the last non-missing measurement prior to administration of the first dose of IMP.

In by-visit summary tables the baseline will be summarised using all available data, but also for each visit using only the baseline data from subjects with available data at the visit; hence the mean change from baseline will equal the mean visit value – mean baseline value.

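### Percentage change in the EASI components has no lower bound on its denominator: for excoriation and lichenification an eligible patient may have no defined value or an extreme one, and SAP 8.2.2 has no rule for either

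*SAP*

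**What the plan says.** SAP 4.2 (EASI Components) builds a score for each of erythema, oedema/papulation, excoriation and lichenification by summing region weight x sign severity x extent grade over the four body regions. It then defines the endpoints: "The secondary endpoints associated with Cohort 3 are percentage change from baseline for each of the EASI components". SAP 8.2.2 gives the analysis: "Percent change from baseline to Week 2 for each EASI component will be analysed for the FAS with an ANCOVA model". The model contains the baseline value and treatment, and it is repeated at Days 5, 8 and 10. Absolute change in the components is summarised but not modelled.

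SAP 6.1 sets the test: "All statistical tests for Cohort 3 will be 1-sided at the 0.05 level of significance and accompanied by a 2-sided 90% CI".

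Other text that bears on the point:

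- Protocol 4.2 and 7.7 require a total EASI of 12 to 48 on Day 1. No component has a minimum.
- Protocol Appendix 11 scores each sign from 0 to 3 and allows half scores.
- Protocol 7.9 defines IGA grade 3, the lowest grade for entry, by erythema and papulation/infiltration. It does not mention excoriation or lichenification.
- SAP 6.2 leaves missing data unimputed unless a specific approach is described. None is described for an undefined component value.
- Protocol 8.2 leaves outlier methods to the SAP or an addendum. The SAP gives none for efficacy.
- The residual check and possible rank transformation stand in SAP 8.1, for the primary endpoint, and are not repeated in 8.2.2.

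**The concern.** A percentage change is a ratio to baseline. For total EASI the denominator cannot fall below 12. For a component it can be zero or close to zero, with two results.

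First, a patient with a zero baseline has no percentage change and drops out of the model. That includes a patient who worsens from zero, so exclusion depends on which signs were present on Day 1. Second, a patient with a very small baseline can show a rise of several hundred percent from a trivial absolute change. With 10 placebo patients, or even 20 active ones, one such value can hide a real effect or create a false one.

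At stake is the reading of the component results, chiefly for excoriation and lichenification, at four time points.

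**Working it through.** **1. The plan's own figure.** SAP 3.3 assumes: "With 20 subjects in the ZPL-5212372 group and 10 subjects in the placebo group"; an SD of 30 percentage points; and an effect of 30 points ("assuming that there is an improvement of at least 30% with ZPL-5212372 compared to placebo"). It concludes that "there is 80% power of obtaining a statistically significant result". The noncentrality is 30 / (30 x sqrt(1/20 + 1/10)) = 2.582. A 1-sided 5% t test then has power 80.9% with 28 degrees of freedom, or 80.8% with 27 (one covariate). The stated 80% is reproduced. It refers to total EASI; the documents give no effect, SD or power for any component.

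**2. Can an eligible patient have a zero component?** Take extent grade 2 (10-29%) in every region. The region weights sum to 0.1 + 0.2 + 0.3 + 0.4 = 1, so EASI = (sum of sign scores) x 2.

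- E = O = L = 2, X = 0: EASI = 6 x 2 = 12.0, excoriation = 0.
- E = O = 3, X = L = 0: EASI = 6 x 2 = 12.0, excoriation and lichenification both 0.
- E = O = 2, X = L = 0 at extent grade 3 instead: EASI = 4 x 3 = 12.0, again both 0.

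The first and third have moderate erythema and papulation, which matches IGA grade 3. All three meet the Day 1 EASI limit.

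**3. How small can a non-zero component be?** The minimum is 0.1 x 0.5 x 1 = 0.05 (head only, half score, extent grade 1).

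- From 0.05 to 0.20 (head, score 1, extent grade 2: 0.1 x 1 x 2): (0.20 - 0.05) / 0.05 = +300%. The absolute change is 0.15 on a 0-18 scale.
- From 0.1 (head, score 0.5, extent grade 2; total EASI 12.1 if added to the first pattern above) to 0.6 (score 1 on head and arms, 0.2 + 0.4): +500%.

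**4. Chance of at least one zero among 30.** This is 1 - (1 - p)^30. The rate p is not in the documents, so a range is assumed.

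| Assumed p | Expected number | P(at least one) |
|---|---|---|
| 2% | 0.6 | 45% |
| 5% | 1.5 | 79% |
| 10% | 3.0 | 96% |

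**5. Effect on the planned ANCOVA.** Simulation: 20 vs 10, response on baseline and treatment, 1-sided 5%. The effect (-30) and SD (30) are borrowed from total EASI. Assumed, and not in the documents: placebo mean -20%, other component baselines uniform on 2 to 8, and the one extreme patient at a baseline of 0.05 or 0.1 (the results agree).

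| Scenario | Mean estimate | Mean SE | Rejection rate |
|---|---|---|---|
| No extreme value, true effect -30 | -30 | 11.7 | 80% |
| One active patient at +100%, true effect -30 | -24 | 15.1 | 43-45% |
| One active patient at +300%, true effect -30 | -16 | 26 | 4% |
| One placebo patient at +300%, no true effect | -26 | 24 | 18-19% (nominal 5%) |

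The size depends on the assumed baselines. With the others uniform on 0.5-6, 2-8 or 3-6, power with one active patient at +300% is 1-2%, 4% or 16-17%.

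**6. Loss of zero-baseline patients.** Dropping 3, 6 or 9 of the 30 at random lowers power from 80% to 75%, 70% or 64% under the same assumptions. Actual loss would follow the baseline sign pattern and need not be random.

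**The case against.** Several points on the other side stand.

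- **Not all four components.** A reader might infer that every component analysis is exposed. Entry requires IGA of at least 3, which is anchored to moderate erythema and papulation, with affected BSA of at least 10%. A zero or tiny baseline on those two signs is implausible.
- **Not certain to happen.** A reader might infer that patients will be dropped or that one will dominate. The documents give no component baseline distribution, so this is a risk of unknown frequency.
- **Not hidden.** SAP 6.1 puts n and the number of missing values in the summary tables, and component scores are listed (Listings 16.2.6.1.2.1 and 16.2.6.1.2.2). The exclusions would be visible, but the model would still omit the patients.
- **Not as extreme as a simple t test suggests.** A t test puts power with one active patient at +300% below 1%. SAP 8.2.2 specifies a baseline covariate, and the extreme patient also has an extreme baseline, so the covariate absorbs part of the outlier. About 4% is the figure for the planned model under the main assumptions.
- **Partly mitigated.** Absolute change is already summarised, so worsening from zero is described. A rank ANCOVA would keep about 66% power with the same outlier, but the SAP provides for that only under the primary endpoint.
- **Secondary weight.** The components are not among the Cohort 3 endpoints in Protocol 2.4; the SAP adds them. No decision rule in the documents uses them.

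Replacement does not close the gap. Protocol 4.8 says that certain withdrawn patients "may be replaced until at least 30 evaluable patients have completed the study", but a patient who completes with a zero baseline still has no percentage change.

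These points narrow the concern. They do not supply a rule for an eligible patient whose endpoint is undefined.

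**Conclusion.** The concern holds for excoriation and lichenification. The endpoint in SAP 4.2 and 8.2.2 is undefined for some patients who meet the entry criteria and unstable for others, and no zero-baseline, outlier or residual-check rule applies to 8.2.2.

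Where a near-zero baseline occurs, one patient can decide the result in either direction: power of about 4% instead of 80%, or a 1-sided error of 18-19% instead of 5%. These figures illustrate the mechanism and do not predict what the trial will show. They rest on total-EASI planning values applied to a component, an assumed placebo mean and assumed baselines. The frequency of such baselines is unknown.

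A reader might extend the point to the primary analysis. The documents do not support that: the Day 1 minimum of 12 protects the total score, and the stated 80% power is reproduced and unaffected. The change should be made, but it concerns secondary results only.

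**What to change.** Before database lock, which SAP section 2 allows, amend SAP 4.2 and 8.2.2 as follows:

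- Make absolute change from baseline in each component score the modelled endpoint, by ANCOVA with baseline component score and treatment, at Week 2 and at Days 5, 8 and 10.
- Keep percentage change as description only, for patients with a non-zero baseline, and report the number excluded by treatment group and component.

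Every FAS patient with a baseline score and an on-treatment score at the visit then contributes. Patients with no such visit score still drop out, because these are observed-case analyses. A move from 0.05 to 0.20 counts as +0.15 instead of +300%. The SAP already models absolute change for pruritus NRS (8.2.4) and BSA (8.2.7).

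The cost is wording in two sections and the titles of the four component ANCOVA tables in SAP section 14. No new data are needed. The downside is that component results are no longer on the percentage scale of the total score. Power on the new scale cannot be stated, because the documents give no component effect or SD.

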### 8.2.3. Investigators Global Assessment (IGA)

IGA will be summarised for the FAS with counts and percentages by treatment at each visit. The number of missing values will also be presented. Shift tables of change from baseline will also be presented with marginal totals.

IGA response will be summarised at each visit with counts and percentages; missing responses will also be tabulated. An exact logistic regression analysis will be performed for Week 2. Baseline IGA, stratification variable (baseline EASI; ≤20 or >20) and treatment will be included in the models as factors; subjects with missing responses will be counted as non-responders. The odds ratio, p-value and associated exact 90% CI will be presented. This analysis will be repeated for IGA success.

### 8.2.4. Numerical Rating Scale (NRS)

NRS for pruritus will be summarised by treatment and visit for the FAS. Summaries will present the descriptive statistics for baseline, change from baseline and percentage change from baseline data.

Change from baseline to Week 2 of the NRS for pruritus will be analysed for the FAS with an ANCOVA model. The model will include baseline NRS, stratification variable (baseline EASI; ≤20 or >20) and treatment. The treatment effect will be estimated with the difference between least square means (LS means), defined as ZPL521 - placebo. The estimate, standard error, 1-sided p-value, and 90% CI will be presented.

This analysis will be repeated for the average change from baseline in NRS pruritus over Days 8, 10 and 15.

Summaries over time will be presented for the FAS for the following NRS endpoints:

SAP Version v2.0 Page 30 of 43

Date: 16th March 2017

- NRS for sleep disturbance
- total duration of itching

All pruritus data will be listed.

### 8.2.5. Verbal Rating Score (VRS)

The VRS will be summarised for the FAS with counts and percentages by treatment at each visit. Shift tables of change from baseline will also be presented with marginal totals.

### 8.2.6. Patient Global Impression of Change (PGIC)

The PGIC scores will be summarised for the FAS with counts and percentages in each treatment group. All data collected will be included.

The PGIC will also be dichotomized into responders, defined as responses of 'Very Much Improved', 'Much Improved' or 'Minimally improved' (1, 2 or 3) and non-responders (4, 5, 6, or 7 plus missing data). The PGIC responder variable will be analysed in the FAS with exact logistic regression. The stratification variable (Baseline EASI; ≤20 or >20) and treatment will be included in the model as factors; the odds ratio, p-value and associated exact 90% CI will be presented.

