### **8.5.2 Secondary Endpoints**

The proportion of subjects who achieve an EASI-50 response (50% reduction in EASI score from baseline) at Week 2 will be compared between the treatment groups. Group proportions and the difference between these proportions will be calculated along with the corresponding 90% confidence interval. These data will also be analysed using logistic regression, including treatment and baseline. The odds ratio and accompanying 90% confidence interval will be presented.

The proportion of subjects who achieve an EASI-75 response (75% reduction in EASI) and the proportion of subjects who are responders for IGA score (reduction from baseline of at least 2 points) at Week 2, will be analysed using the same analyses described for the EASI-50 response. The changes from baseline in IGA score will also be summarized using categorical shift tables.

The changes from baseline in body surface area, pruritus NRS score for worst itch, NRS score for sleep disturbance and duration of itching at Week 2 will be analysed using the same analyses described for the primary analysis.

The changes from baseline in VRS score will be summarized using categorical shift tables.

The PGIC score will be summarized and analysed using logistic regression, presenting odds ratios and associated 90% confidence intervals for the comparison between treatment groups.

Secondary endpoints will be analysed using the Full Analysis Set.

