### Patient Global Impression of Change (PGIC)

At the end of treatment (Day 15 or Early Termination Visit) subjects in Cohort 3 will be asked to rate their degree of improvement (or worsening) of their AD compared to before the start of treatment with study drug, using a 7-point scale. The scale ranges from 1 (very much approved) to 7 (very much worse).

The PGIC will be dichotomized into responders, defined as responses of 'Very Much Improved', 'Much Improved' or 'Minimally improved' (1, 2 or 3 on the scale above) and non-responders (4, 5, 6, or 7 on the scale above, plus missing data).

SAP Version v2.0 Page 18 of 43

Date: 16th March 2017

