#### 12. CHANGE FROM ANALYSIS PLANNED IN PROTOCOL

The changes from the analyses specified in the protocol are:

- 1. The definition of responders for IGA score in the protocol has been further clarified and made consistent with the sponsor's previous atopic dermatitis study. The definition has changed from reduction from baseline of at least 2 points, to those subjects who achieve a score of 'Clear' or 'Almost clear', or a reduction of ≥ 2 from baseline. An additional definition of IGA success has also be defined as those subjects who achieve a score of 'Clear' or 'Almost clear'.
- 2. The protocol stated that the changes from baseline at Week 2 in NRS sleep disturbance and duration of itch will be analysed using ANCOVA, however it has been decided that it is sufficient to only summarize these endpoints by treatment group and visit. Only the NRS endpoint daily pruritus will be analysed.
- 3. The protocol stated that the Draize score for Cohort 1 would be summarised by treatment group and the change from baseline in Draize score would also be summarised using categorical shift tables. However, the safety review of Cohort 1 showed that there were very few changes in Draize score; it was therefore decided that summaries were not necessary for this endpoint and the data would only be listed.
- 4. The PK analyses described in the protocol have been modified to reflect the very low and sporadic systemic exposure observed during the safety review meetings for Cohorts 1 and 2.

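### The PGIC is tested only as improved versus not improved; with 20 v 10 patients, a test on the seven-point score would use the data better

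*SAP*

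**What the plan says.** Protocol 7.11 asks Cohort 3 patients once, at Day 15 or early termination, to rate change since the start of dosing on seven grades, from *Very Much Improved* (1) to *Very Much Worse* (7). Protocol 8.5.2 gives the analysis in one sentence: "The PGIC score will be summarized and analysed using logistic regression, presenting odds ratios" with 90% confidence intervals. It states no cut point and does not say whether the model is binary or ordinal.

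The SAP sets the cut. Section 4.2 says "The PGIC will be dichotomized into responders", and 8.2.6 repeats it: "The PGIC will also be dichotomized into responders, defined as responses of 'Very Much Improved', 'Much Improved' or 'Minimally improved' (1, 2 or 3"). Grades 4 to 7 and missing data count as non-response. The model is exact logistic regression on the FAS with treatment and EASI stratum (≤20, >20) as factors. SAP 8.2.6 also tabulates the seven grades by treatment group (Table 14.2.6.1), without a test.

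For all Cohort 3 testing, SAP 6.1 says "All statistical tests for Cohort 3 will be 1-sided at the 0.05 level of significance and accompanied by a 2-sided 90% CI". SAP Section 12 opens "The changes from the analyses specified in the protocol are" and lists four items: the IGA responder definition, sleep disturbance and itch duration, the Draize score, and PK. The PGIC is not among them. Neither document gives a reason for the cut.

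**The concern.** The PGIC is the trial's only patient global rating. In the test, *Very Much Improved* counts the same as *Minimally Improved*, and *No change* the same as *Very Much Worse*. A cut at the mildest grade of improvement separates the arms badly if many placebo patients reach that grade, and there are reasons why some might:

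- Placebo has the same excipients as the active ointment (Protocol 5.3).
- Day 1 follows at least a week without topical steroids or calcineurin inhibitors (Protocol Table 6).
- Entry requires EASI of at least 12 and IGA of at least 3 on Day 1 itself (Protocol 4.2), which invites regression to the mean.

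At stake is the reading of a secondary endpoint. A real shift towards the better grades could leave the responder proportions close and the exact interval very wide, and the result could be taken to mean that patients noticed no benefit.

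**Working it through.** **Inputs from the documents.** 20 active, 10 placebo; one-sided 5% (SAP 3.3, 6.1). Seven grades, cut at 3 (SAP 8.2.6).

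**Assumed inputs.** The placebo PGIC distribution and the PGIC effect. Neither is given, so ranges are shown. The 1.0 SD shift is borrowed from the EASI planning effect (30/30).

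**1. The plan's own figure.** SAP 3.3: "With 20 subjects in the ZPL-5212372 group and 10 subjects in the placebo group, there is 80% power of obtaining a statistically significant result", assuming "an improvement of at least 30% with ZPL-5212372 compared to placebo" and "a standard deviation for the percentage changes from baseline between subjects of 30"%. Noncentrality = 30 / (30 × √(1/20 + 1/10)) = 1/√0.15 = 2.58. Normal approximation: Φ(2.58 − 1.645) = Φ(0.94), about 82.6%. Noncentral t: 80.9% (28 df) or 80.8% (27 df). The stated 80% reproduces. It concerns EASI; no power is stated for the PGIC.

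**2. What the dichotomy needs to reach p ≤ 0.05.** A one-sided Fisher test serves as an unstratified proxy for the planned exact model. This step needs no assumed distribution.

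| Placebo responders of 10 | Active responders of 20 needed |
|---|---|
| 3 | 14 |
| 5 | 18 |
| 6 | 19 |
| 7 | 20 |
| 8 or more | not reachable |

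The limit is simple to verify. With 20/20 v 7/10, p = C(10,3)/C(30,3) = 120/4060 = 0.030. With 20/20 v 8/10, p = C(10,2)/C(30,2) = 45/435 = 0.10.

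**3. Power under assumed distributions.** PGIC is treated as a cut-up latent normal variable. For each grade, active cumulative proportion = Φ(Φ⁻¹(placebo cumulative proportion) + shift). For example, with 50% on placebo and a shift of 1.0, active response is Φ(0 + 1.0) = 84%. Assumed placebo proportions in grades 1–2 were 10, 20, 30, 40 and 50% for the five rows. Binary cuts: Fisher, full enumeration. Seven grades: one-sided tie-corrected rank test, 3,000 simulated trials per scenario.

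| Assumed placebo, grades 1–3 | 1.0 SD: SAP cut | 1.0 SD: cut at 1–2 | 1.0 SD: 7 grades | 0.6 SD: SAP cut | 0.6 SD: cut at 1–2 | 0.6 SD: 7 grades |
|---|---|---|---|---|---|---|
| 30% | 53% | 34% | 77% | 22% | 8% | 42% |
| 50% | 46% | 49% | 76% | 22% | 17% | 41% |
| 60% | 40% | 53% | 76% | 19% | 22% | 41% |
| 70% | 33% | 51% | 76% | 16% | 23% | 41% |
| 80% | 21% | 46% | 73% | 12% | 22% | 40% |

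Share of the seven-grade power kept by the SAP cut at 1.0 SD: 53/77 = 69%, 46/76 = 61%, 40/76 = 53%, 33/76 = 43%, 21/73 = 29%. At 0.6 SD: 22/42 = 52%, 22/41 = 54%, 19/41 = 46%, 16/41 = 39%, 12/40 = 30%.

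**4. How much of the gap is the exact test.** Under the null the exact test on the dichotomy rejects about 2–3% of the time, against about 4–5% for the rank test. A stratified simulation (20 v 10, common odds ratio 4, assumed placebo response 40 / 50 / 65 / 75%) gave power of 42 / 36 / 27 / 20% for the exact test on the SAP cut, 53 / 48 / 39 / 28% with a mid-p value on the same cut, and 60–63% for the stratified rank test. Taking the rank test as 62 / 61 / 60 / 60%, the share of the gap removed by mid-p is 11/20 = 55%, 12/25 = 48%, 12/33 = 36% and 8/40 = 20%. So conservatism explains about half the gap at 40–50% placebo response and less above that; the rest comes from collapsing the grades.

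**The case against.** - **The protocol may already mean a binary outcome.** Protocol 8.5.2 uses logistic regression for the EASI-50, EASI-75 and IGA responders too, and Protocol Section 8 leaves detailed methods to the SAP. A reader might infer an undeclared change from protocol. The documents do not support that: the protocol sentence fits a binary or an ordinal model. What stands is narrower. Section 12 records a clarified IGA responder definition, so the PGIC definition belongs there as well.
- **The full scale is not dropped.** The seven grades are tabulated by arm, so a shift towards *Much Improved* would be visible. This stands; the loss is confined to the test and its odds ratio.
- **High placebo response is not documented.** A reader might infer that placebo patients easily reach grade 3. Protocol 1.4 treats the placebo change as something the study is to establish. Emollient starts at least 7 days before Day 1, so part of its benefit may precede baseline. SAP 3.5 directs it to affected areas not treated with study ointment. Protocol 3.1 expects flares after withdrawal of usual medication, and no rescue medication is provided, so worsening on placebo is also plausible. This stands, and is why a range is shown.
- **The level of the cut is not the fault.** At 30% placebo response the SAP cut beats a *Much Improved* cut (53% v 34%), and at 50% they are about equal. This stands.
- **The comparison favours the ordinal method.** Data were generated under a latent shift or a common odds ratio, which suits it. This is fair; the size of the advantage is illustrative.
- **The endpoint is secondary and unpowered.** Worst itch is also patient-reported and is tested twice by ANCOVA (SAP 8.2.4), so the patient's view does not rest on the PGIC alone. This stands, and limits the consequence.

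**Conclusion.** The point holds as a cheap improvement. The only planned PGIC test reduces seven grades to two and applies a conservative exact method to 30 patients. The seven-grade rank test had more power in every scenario examined: about 76% against 53% to 21% at a 1.0 SD shift, and about 41% against 22% to 12% at 0.6 SD, for assumed placebo response of 30% to 80%. With 8 or more placebo responders, the unstratified Fisher proxy cannot reach significance at all.

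A reader might infer that the endpoint loses most of its ability to separate the arms. At a 1.0 SD shift that is so only if placebo response is about 70% or more (60% or more at 0.6 SD), and the documents give no such rate. *A substantial part* is the supportable wording.

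These figures rest on assumed placebo distributions, a latent-normal shift borrowed from EASI, and unstratified proxies for the planned models. The Fisher limits in step 2 rest only on the sample sizes and the one-sided 5% level. The primary EASI analysis is unaffected.

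**What to change.** In SAP 8.2.6, make the treatment comparison an analysis of the seven-point score on the FAS. Name one method in advance:

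- proportional-odds logistic regression with treatment and EASI stratum, giving an odds ratio, one-sided p-value and 90% CI; or
- a stratified Wilcoxon (van Elteren) test by EASI stratum.

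The first keeps the odds ratio that the protocol asks for; the second avoids the proportional-odds assumption. Treat a missing PGIC as the worst category.

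Keep the present grades 1–3 responder analysis as supportive, and align SAP 4.2. The proportion at *Much Improved* or better may be shown descriptively, but that cut should not replace the current one as the test, because it is worse at low placebo response. Add a line to Section 12 recording the PGIC definition and analysis.

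The cost is one paragraph, one table and one Section 12 entry, using data already collected. The downsides are the proportional-odds assumption and reliance on asymptotic inference with 30 patients; the retained exact responder analysis gives a check on the latter.
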